As a minimal risk study, there will be no change in the routine care of these patients.

Definition of hemodynamic deterioration - any of:

- A significant period (greater than 5 min.) of systolic blood pressure less than 90 associated with a heart rate greater than 110.
- 20% increase in HR from baseline
- 15% decrease in MAP from baseline
- Clinician defined need for greater than established initial fluid resuscitation (blood products intended to maintain blood pressure)
- A blood lactate result greater than 4 without nontraumatic causes of lactic acidosis

Study Design: Prospective Case Cohort

- Screening for enrollment will be undertaken in the Emergency Department (ED).
- Patients will be assigned a de-identified Research **Subject Number**
- Please note that at the discretion of the clinical study team, less than the complete ensemble of noninvasive sensing technologies may be utilized in specific cases based on patient comfort and clinical circumstances.

Placement of Sensing Technologies

[figure not shown]
- After confirmation of inclusion criteria, the absence of exclusion criteria, and informed consent is documented, trained research personnel will apply all sensors described below to appropriate locations on the patient's skin.
- Patients will already have undergone application of the ECG and pulse ox plethysmography disposables as part of normal clinical monitoring. These will be left in place and the ECG and plethysmography data will be shared with our prototype data collection system in a manner that does not interfere with the clinical monitor electrodes. The study monitor data will be acquired via iCollect software manufactured by GE. The software collects biometric data (e.g. EKG, SpO2) from clinical monitors without any imbedded PHI.

- Two SwissTom EIT arrays will be placed per subject: 1) around the thorax at the anatomic nipple line, and 2) the second alternating patient to patient between the upper abdomen at the level of the liver-spleen and the proximal thigh at the femur mid-shaft.
- **NIRS** – 3 locations, 1 probe per location: upper chest in region of thoracic EIT, and 1 either upper thigh or upper arm.
- Three sets of four ScioSpec EIS electrodes (I+, V+, V-, I-). V electrodes are placed medially to I electrodes.
 - 1st set – is applied on the torso just above the upper SwissTom arrays, I+ and V+ on the right mid-axillary line and V- and I- on the left mid-axillary line.

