 - 2nd set – is applied between the upper and lower SwissTom arrays adopting the same positioning technique as set one with respect to the mid-axillary line. In patients with the 2nd SwissTom array on the thigh, the 2nd ScioSpec EIS is also applied in this same truncal location.
 - 3rd set – applied on the right upper arm, “+” leads on the outside of the arm and “-“ leads on the inside, sandwiching the bicep.
- Please see device descriptions on pg. 12 for further detail

System Setup

CLINICAL MONITOR		
1. Clinical monitor: Open the desktop icon “iCollect - shortcut”	 iCollect - Shortcut	

2. At the following menu, ensure the settings in the orange box are as shown below and click “Online”

Patient Case Methods

- Research team member will turn on device and enter study identifier data.
- Research team member applies the device sensors as per Appendix II
- Research team member will confirm that data is being acquired.
- Device will remain attached to each patient until any of the following:
 - Stable for 6 hours (no signs of hemodynamic deterioration)
 - Disposition via discharge from the ED or admission to a care unit
 - Development of change from baseline hypotension or tachycardia below or above limits respectively.
 - The patient wishes for the device to be removed.
- The following data will be collected from the sensors: heart rate and electrical activity via electrocardiogram, transcutaneous oxygen saturation, blood pressure and arterial waveforms via finger plethysmography. Lastly, sensor data will collect changing perfusion physiology via electrical impedance tomography system.
- The study coordinator will extract relevant data from the patient's chart to complete a case enrollment form.
 - Data points from chart-
 - Gender

- Age (by decade)
- Height
- Weight
- Medications given during the ED visit and admission (if patient is admitted)
- Vital signs at triage and at “change in status.”
- Based on clinical chart review, the PI and co-PI will independently adjudicate each patient into either the “likely ongoing hemorrhage” or “likely no ongoing hemorrhage” outcome categories without reference to the algorithm results. In the event of differing results, the PI and the co-PI will meet and discuss until consensus is reached.
- At the quarterly milestones the existing data will be used iteratively to refine the Phase II algorithm, creating an initial Phase III algorithm.

Data Acquisition and Storage:

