SwissTom Impedance Tomography, NIRS Spectroscopy and ScioSpec Bioimpedance raw signals are all stored in a live, streaming fashion directly on an internal hard drive. All of this data is non-PHI and completely de-identified – only the subject number is incorporated into the file name. Similarly, any data collected by iCollect (mentioned above) has absolutely no PHI embedded within it and is live-captured and saved on an internal hard drive. At the end of the experiment all of this non-PHI, de-identified data will be uploaded to a secure cloud-based drive that has been approved by the participating institutions.

Data Analysis

At the completion of the study, the full data set will be used to define the performance of the Phase II algorithm with respect to the pre-specified performance criteria.

Data analysis will include the following steps:

- 1) **Data cleaning, filtering and validation:** All data will be processed to ensure that patterns are consistent with the underlying physiology. Any physiologically incorrect data will indicate issues related to loose electrodes, malfunctioning sensors,

etc. Such data will be filtered and cleaned to ensure that only meaningful data is used for algorithm testing.

- 2) **Data transformation and feature generation:** The cleaned, validated data will be transformed through a series of processing steps to generate the necessary features to be used in the supervised machine learning algorithms as predictors.
- 3) **Classification:** The features will then be used to generate machine learning-based predictions. These predictions will be compared against the ground reality of the patient's status to evaluate the algorithm performance.

Algorithm Performance Criteria: the algorithms developed will be trained to alarm under two circumstances indicating significant risk of ongoing hemorrhage progressing to shock: 1) a change from baseline, 2) development of prespecified patterns.

Performance will be judged on the basis of:

1. time of alarm before onset of deterioration
2. sensitivity, specificity, PPV, NPV for alarm/no alarm outcome
3. ROC curve and AUC for alarm/no alarm outcome
4. false-positive and false-negative rates

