Power and Sample Size: We anticipate acquiring data from every enrolled subject. Power and sample size calculations indicate that a sample size of 480 subjects should be sufficient to: 1) further identify the minimal subset of noninvasive measurement technologies necessary for the desired diagnostic performance, 2) validate the existing algorithms, and 3) initially train a human clinical iteration of the algorithms, with a sufficient degree of accuracy ($p < 0.05$ for ROC-AUC).

Enrolled patients will undergo standard electrocardiogram (3-lead) and oxygen saturation continuous monitoring.

In addition to these standard physiologic measurements, as a part of research, we will also acquire the following non-invasive optical and impedance measurements. All of these devices have been previously validated as non-invasive and safe in humans.

The clinicians providing care to the patient will be blind with respect to the measurements from these devices.

General Approach to Minimize Risk

This protocol will be minimal risk to patients as all these technologies have been robustly demonstrated to be safe (see below). There is minimal risk associated with placement of these devices and they can be removed at any time. They don't interfere with standard equipment used in clinical management of trauma patients. As described above, clinical management of the patient will not be affected by the study intervention.

Protection: Each subject will give informed consent after all questions have been answered by a study team member. Confidentiality of data will be assured by study specific coding of subject identities. No identified individual data will be presented or published; rather, group mean data will serve as the basis for comparisons. Procedures used in this study are performed regularly in the clinical setting by the investigators.

Any original signed paper consent documents, as well as any hard copy of study documents will be stored in a locked cabinet at Baystate Medical Center. Any electronic patient information will be stored on REDCap, a secure online database that is password-protected and only accessible by study personnel.

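### The algorithm is tested only on data kept by a cleaning step with no set rule, and lost signal is not accounted for, so sensitivity, alarm lead time and AUC may be overstated

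*Combined protocol and SAP*

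**What the plan says.** The Data Analysis section opens by saying that "the full data set will be used to define the performance of the Phase II algorithm". Step 1 (data cleaning, filtering and validation) then narrows what is tested:

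- The criterion: "All data will be processed to ensure that patterns are consistent with the underlying physiology".
- The cause assumed for data that fail it: "Any physiologically incorrect data will indicate issues related to loose electrodes, malfunctioning sensors".
- The consequence: "Such data will be filtered and cleaned to ensure that only meaningful data is used for algorithm testing".

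The performance measures that follow are alarm time before deterioration, sensitivity, specificity, PPV, NPV, ROC-AUC, and false-positive and false-negative rates. None reports how much data, or how many patients, could not be evaluated.

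Three other places bear on the point. Study Design allows that "less than the complete ensemble of noninvasive sensing technologies may be utilized in specific cases based on patient comfort and clinical circumstances". Power and Sample Size states "We anticipate acquiring data from every enrolled subject". On blinding, Patient Case Methods has the adjudicators assign patients to "outcome categories without reference to the algorithm results", and the text after the sample-size paragraph adds "The clinicians providing care to the patient will be blind with respect to the measurements from these devices". Neither statement covers the people who clean the signals.

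**The concern.** The intended product watches stable patients continuously and automatically. In use, a period without usable signal is a period in which no alarm can sound. Under step 1 as written, that period can leave the test data, and the resulting miss need not be counted.

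The criterion makes this more than a formality. The algorithm is meant to alarm on a change from baseline, so unusual physiology is its target. A judgement about whether a pattern is physiologically credible, with no numerical rule behind it, could remove some of the signal being sought. Step 1 names only equipment or contact faults as the explanation for data that look wrong.

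Splitting patients into training and test sets would not solve this, because the filter is applied to the test data. At stake is whether the reported figures describe everyone who wore the device, or only those stretches of recording that someone judged usable.

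**Working it through.** **The plan's own figure.** The only relevant figure is 480 subjects, said to suffice for p < 0.05 on ROC-AUC. It cannot be reproduced, because no event rate, null AUC, target AUC, power or sidedness is given. A grid using the Hanley-McNeil variance found twelve unrelated combinations within 3% of 480. Two examples are AUC 0.70 against 0.80 at 20% prevalence with 90% two-sided power (475), and 0.75 against 0.90 at 5% prevalence with 80% two-sided power (484). Nothing about expected data loss can be read back from the 480.

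**What step 1 leaves open.** The documents give no artefact threshold; no unit of removal (segment, channel or patient); no automated or locked pipeline; no minimum evaluable recording; no rule for a patient left without signal; no count of removals by outcome; and no all-enrolled analysis. The one numerical quality check, EIS impedance below 1,000 ohm in Appendix II, is a bedside set-up step for a single sensor.

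**Inputs for the illustration.** All are assumed, since the documents supply none: sensitivity in evaluable patients 0.90 (or 0.80), specificity 0.80, AUC 0.80 or 0.90, and a fraction u of 5%, 10% or 20% wholly unevaluable in the group concerned. Over all 480 these fractions would be 24, 48 or 96 patients.

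**Sensitivity**, with unevaluable bleeding patients counted as missed, is Se(all) = Se(evaluable) × (1 − u). **Specificity** depends on the rule for unevaluable non-bleeding patients: counted as failures, Sp(all) = Sp × (1 − u); counted as no alarm, Sp(all) = Sp × (1 − u) + u.

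| u | Se from 0.90 | Se from 0.80 | Sp from 0.80, failures | Sp from 0.80, no alarm |
|---|---|---|---|---|
| 5% | 0.855 | 0.76 | 0.76 | 0.81 |
| 10% | 0.81 | 0.72 | 0.72 | 0.82 |
| 20% | 0.72 | 0.64 | 0.64 | 0.84 |

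A no-alarm rule thus lowers sensitivity and raises specificity. Used alone, it would flatter specificity.

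**AUC.** Take a binormal model with separation d = √2 × z(AUC), and suppose the removed patients' scores would have been uninformative (centred at d/2 in both classes). Then AUC(all) = (1 − u)² × A + 2u(1 − u) × Φ(d/(2√2)) + u² × 0.5.

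- A = 0.80: Φ(0.421) = 0.663. At u = 20%, 0.64 × 0.80 + 0.32 × 0.663 + 0.04 × 0.5 = 0.744. At 5% and 10% the results are 0.786 and 0.772.
- A = 0.90: Φ(0.641) = 0.739. At 5%, 10% and 20% the results are 0.884, 0.867 and 0.832.

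A simulation with 200,000 per class agrees within 0.001. If removal is unrelated to both outcome and score, AUC among retained patients equals AUC among all.

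**Outer bound.** If cleaning were done with outcomes known and happened to remove the worst-ranked 5%, 10% or 20% in each class, a true AUC of 0.80 would appear as 0.864, 0.913 or 0.981. This shows why blinding should be stated. It does not predict what will happen here.

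**Alarm lead time.** No figure is possible. Lead time would be measured on retained signal only, and the plan does not say how a deterioration preceded by discarded signal enters the summary.

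**The case against.** Filtering test data is not an error in itself. If the same locked quality filter ran in training, testing and eventual use, testing on filtered signal would be proper. That stands; the defect is that the plan does not say the filter is of this kind.

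Four stronger readings are tempting, and the documents do not support them.

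- *That cleaning is done with outcomes known.* The plan is silent. Signal files carry only a subject number, and outcome is adjudicated from chart review. Equally, the algorithms are supervised and refined each quarter on accumulating data, so labels may well be in use before the final test. The question is open either way.
- *That accuracy is overstated.* This is not shown. Removal unrelated to outcome and score leaves AUC unchanged, and nothing in the documents says how signal loss relates to how unwell a patient is. Nor does step 1 say that abnormal physiology is removed: a falling pressure is abnormal without being incorrect. Its removal is a risk of a vague criterion and is not the stated rule.
- *That patients are dropped.* The text speaks of filtering data. Each subject is planned to have two EIT arrays, three EIS sets, NIRS probes, ECG and plethysmography, and staff confirm acquisition and check contact. Losing a channel or segment need not make a patient unevaluable, so the table above is a patient-level extreme for each u.
- *That the sample-size text contradicts the allowance for fewer sensors or early removal.* Acquiring some data from every subject is compatible with both.

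**Conclusion.** The concern holds as a risk of unknown size. Testing is restricted to data kept under an open-ended plausibility criterion, with no prespecified rule, no stated blinding of the cleaners, and no accounting for patients or periods without usable signal. Sensitivity, alarm lead time and AUC may therefore be overstated for the patients monitored.

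On assumed inputs, sensitivity of 90% among evaluable bleeding patients corresponds to 85.5%, 81% or 72% among all bleeding patients when 5%, 10% or 20% are wholly unevaluable and counted as missed. An AUC of 0.80 corresponds to between 0.786 and 0.744 over the same range if the lost scores would have been uninformative. The direction for specificity depends on the counting rule. A reader might infer that the results will certainly be biased in the algorithm's favour; the documents do not establish that. They also contain nothing that would allow the bias to be excluded or measured.

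**What to change.** 1. Code an automated signal-quality rule, with thresholds for each sensor, the unit of removal and the minimum evaluable recording. Lock it before outcome labels are linked to the validation data, and run it without outcome labels or algorithm predictions. Because accumulating data are used each quarter, state how the lock date relates to those milestones.
2. Report the proportion of patients and of recording time removed, by outcome group and by sensor.
3. Alongside the clean-data result, report performance for all patients with the device applied. Count unevaluable bleeding patients as missed. Show specificity with unevaluable non-bleeding patients taken both as no alarm and as failures, because a no-alarm rule alone raises specificity. State how lost signal before a deterioration enters the lead-time summary.

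The cost is SAP wording, the work of locking the code, and extra tables. Reported sensitivity may be lower. No change to recruitment, device placement or patient care is needed.

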Official Title:	Trauma Study: Early Warning of Progression Toward Hemodynamic Deterioration After Trauma
NCT number:	NCT04912232
Document Type:	Study Protocol and Statistical Analysis Plan
Date of the Document:	7/18/2022 (Protocol)

**Continued Development of a Multiplex Precision Medicine System
for Early Warning of Progression Toward Hemodynamic
Deterioration After Trauma (V3.0)**

Human Trauma Effectiveness Study (n=480)

Site Principal Investigator: [name] MD

Project Principal Investigator: [name] MD

Sponsor: United States Department of Defense

Site: University of Massachusetts Baystate Medical Center

Introduction

This study is **Phase 3** of a three-year DOD CDMRP funded project for development of a multi-technology poly-anatomic noninvasive system for early detection of occult hemorrhage that may be progressing toward hemodynamic instability.

Background

Early detection of ongoing hemorrhage (OH) before onset of shock is a universally acknowledged great unmet need, and particularly important after trauma.^{1,2} Delays in the detection of OH are associated with a “failure to rescue” and a dramatic deterioration in prognosis once the onset of clinically frank shock has occurred. An early alert to the presence of OH with an acceptable rate of false-positives and false-negatives would save countless lives. Additionally, such technology would save critical time, money and effort by allowing medical resources to be applied more accurately – the essence of precision medicine. An automated system would monitor currently stable patients continuously, leaving clinicians free to care for patients in need of attention.

It is widely appreciated that the classic medical vital signs perform poorly until late in the progression to shock after traumatic injury.^{3,4} Currently available techniques, including intermittent vital sign monitoring, laboratory analysis, and single measurement devices have inferior performance before clinically obvious physiologic distress.^{3,5} The overall goal of this project is to develop a multi-technology noninvasive system for early detection of ongoing hemorrhage. The underlying hypothesis is that deep-learning developed algorithms obtaining diagnostic signals from multiple sources will outperform single technology solutions.

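### Lead time to deterioration can be earned by an alarm that only tracks heart rate or pressure, and the plan specifies no vital-sign benchmark that would show it

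*Combined protocol and SAP*

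**What the plan says.** **Inputs.** The Mark I sensor list includes ECG and plethysmography. The prototype description says both subsystems are integrated to supply data for machine learning, and both remain in the list of technologies kept after pruning. Patient Case Methods lists the sensor data as "heart rate and electrical activity via electrocardiogram, transcutaneous oxygen saturation, blood pressure and arterial waveforms via finger plethysmography", together with impedance tomography. No feature list is given.

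**Endpoint.** The Definition of hemodynamic deterioration is met by any one of five criteria. Two of them are "20% increase in HR from baseline" and "15% decrease in MAP from baseline", each sufficient alone and without a required duration. A third combines low systolic pressure with a raised heart rate. The other two are a clinician-defined need for more than the initial resuscitation, and a raised lactate.

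**Alarm and measures.** Under Algorithm Performance Criteria the alarm is trained to respond to "1) a change from baseline, 2) development of prespecified patterns". The first measure is how long before deterioration begins the alarm sounds. The others (sensitivity, specificity, predictive values, AUC, false-positive and false-negative rates) name no reference standard. Data Analysis says only that predictions are compared with the patient's actual status.

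**Second outcome.** In Patient Case Methods, two investigators classify each patient from the chart for ongoing hemorrhage, blind to the algorithm.

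**Purpose.** The Background says that "classic medical vital signs perform poorly until late in the progression to shock", and gives as hypothesis that algorithms using several sources do better than any one technology.

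**The concern.** For events that qualify on heart rate or MAP alone, the endpoint is a threshold on a signal that the algorithm can also see. An alarm that responds to a smaller change in that signal will sound before the event and collect lead time, whether or not it carries any information about bleeding beyond what the bedside monitor already displays.

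Nothing specified in the plan would separate this from real early warning. There is no heart-rate or pressure benchmark, no analysis with these features removed, and no breakdown by the criterion that was met. At stake is what a reported validation would mean. It could not show that impedance or NIRS adds to standard monitoring, which is the rationale for the device, and it would not test the stated hypothesis about single technologies.

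**Working it through.** **1. The plan's own figure.** The section Power and Sample Size states that "Power and sample size calculations indicate that a sample size of 480 subjects should be sufficient to" meet three aims, at p < 0.05 for the AUC. Power, null AUC, target AUC and event prevalence are not given, so 480 cannot be reproduced. If the test is of one AUC against 0.5 (two-sided 0.05, Hanley-McNeil variance), the required N runs from 11 (AUC 0.97, prevalence 30%, power 80%) to 4,600 (AUC 0.60, prevalence 2%, power 90%). Some assumed combinations fall near 480 (466 and 473, for example), but nothing in the plan singles them out. A test against 0.5 would in any case say nothing about vital signs.

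**2. Overlap of input and endpoint.**
- Three of the five criteria are pure heart-rate or pressure thresholds, and two of these need only one signal.
- A heart rate that reaches +20% must reach any lower threshold earlier or at the same reading. With a baseline of 80 bpm as an illustration, 80 × 1.15 = 92 and 80 × 1.20 = 96, so an alarm at +15% sounds at 92 or above and the event is declared at 96.
- That ordering is a logical necessity, not an empirical result. What it costs in false alarms, and how much lead it yields, depend on the traces.

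**3. How much lead a heart-rate-only alarm collects.** The inputs are all assumed: 6-hour heart-rate traces, 20,000 patients per scenario, about 10% drifting upward (0.2-0.5% or 0.5-1.5% of baseline per minute), autocorrelated noise with SD 2-5% of baseline. The event is heart rate at +20% on the same trace.

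| Alarm threshold | Alarm strictly before event | Median lead (min) | Specificity |
|---|---|---|---|
| +10% | 100% | 10-40 | 28-100% |
| +12% | 100% | 8-25 | 57-100% |
| +15% | 99.8-100% | 4-14 | 88-100% |

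Credit for lead time is close to certain on these events. Good specificity is not. A lower threshold buys lead at the price of false alarms, so lead times can be compared fairly only at equal specificity.

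**4. What a benchmark could resolve at N = 480.** For an AUC of A with n1 events and n0 non-events:

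Var(A) = [A(1−A) + (n1−1)(U−A²) + (n0−1)(V−A²)] / (n1·n0), with U = A/(2−A) and V = 2A²/(1+A).

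At an assumed prevalence of 10%, n1 = 48 and n0 = 432:
- A = 0.80: variance = (0.16 + 1.25 + 30.65)/20,736 = 0.001546, SE 0.0393.
- A = 0.90: variance = (0.09 + 0.38 + 18.37)/20,736 = 0.000909, SE 0.0302.
- Paired difference, assumed correlation 0.5: variance = 0.001546 + 0.000909 − 2(0.5)(0.0393)(0.0302) = 0.00127, SE 0.0356.
- Power = Φ(0.10/0.0356 − 1.96) = Φ(0.85) = 80%. The 95% interval for the difference is ±1.96 × 0.0356 = ±0.07.

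Power of the paired test over assumed prevalences:

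| Benchmark vs full algorithm | 2% | 5% | 10% | 20% |
|---|---|---|---|---|
| 0.80 vs 0.90 | 25% | 52% | 80% | 97% |
| 0.80 vs 0.85 | 9% | 16% | 26% | 45% |

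**The case against.** There is a fair case on the other side.

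- *Beating vital signs is not a listed aim.* This is correct. The Phase III summary lists three aims: evaluate the prototype, validate the Phase II algorithm, and re-train it. A reader might infer that the trial fails to test a declared objective of superiority over vital signs. The documents do not support that, since the statement about vital signs is background rationale. The hypothesis that is stated, about single technologies, nevertheless has no comparison among the performance measures.
- *Adjudicated hemorrhage may be the reference for sensitivity, specificity and AUC.* This too is correct, and against that outcome a heart-rate alarm gets no automatic credit. A reader might infer that sensitivity and AUC are inflated by construction. The plan does not say enough to support that. The adjudicated outcome is not fully separate either, because the chart data include vital signs at triage and at a change in status.
- *Heart rate and pressure as features are inferred.* They are collected sensor data from subsystems intended for machine learning, which makes the inference strong but not certain. The progress report credits impedance tomography with most of the accuracy, at an AUC above 80% by itself. That evidence is preclinical, but it argues against concluding that the algorithm merely follows heart rate. The point is that the plan could not tell.
- *An alarm moments before onset would show as near-zero lead.* True, since lead time is itself reported. For that reason a minimum lead is not the essential remedy, and it would not exclude a slow heart-rate drift anyway.
- *The minimal-subset aim invites an ablation.* It does, but no such analysis is specified.

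**Conclusion.** The point holds in a limited form. Lead time, the first performance measure, runs to an endpoint that heart rate or MAP alone can trigger, and nothing in the plan stops an alarm on the same signals from earning that credit. Sensitivity and AUC share the problem only if the same deterioration events are their reference standard, and this is left unstated. The absence of a vital-sign benchmark is plain from the text.

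The size for real patients cannot be derived from the documents. Under the assumed traces, almost every heart-rate-defined event is preceded by a heart-rate-only alarm, with median lead of 4-40 minutes and specificity anywhere from 28% to 100%. These figures rest on the assumed noise and drift, on an event timed from the same trace, and on one of the five criteria. The share of events that will qualify on heart rate or MAP alone is unknown.

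**What to change.** Under Algorithm Performance Criteria:

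1. Name the reference standard for each measure: the defined deterioration event for lead time, and either adjudicated hemorrhage or the deterioration event, stated explicitly, for sensitivity, specificity, predictive values, AUC and error rates.
2. On all patients, with the same events and non-events, report three results side by side: the full algorithm, an HR/BP-only model or threshold alarm, and the algorithm with heart-rate- and pressure-derived features removed. Give paired differences in AUC, and in lead time at matched specificity, with confidence intervals. Fix the benchmark before outcomes are reviewed. Train any fitted comparator on the same development data as the version it is compared with.
3. Report results separately for events that qualify on heart rate or MAP alone and for events that meet other criteria, using the same non-events for both groups.

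A minimum lead time may be added as a sensitivity analysis. The documents offer no basis for a particular value.

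The cost is a few extra model runs on data already recorded, with no change to patient care. Reported performance may look less favourable. If events are few, the paired differences will be imprecise: at 5% prevalence (24 events), power is about 52% even for 0.80 against 0.90. They should therefore be presented as estimates with intervals and not as pass-or-fail tests.
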